**8.0 Study Endpoints:**

**8.1** The primary study endpoint will be the completion of all analysis of the Aims. A secondary study endpoint will be when all patient interviews are completed (n=700).

Table 4. Study Measures and Outcomes		Interview Timepoint				
Variable	Instrument(s) or Measure(s)	BL	6w	6m	12m	18m
Covariates		IP			IP	
Socio-demographics, patient characteristics	Age, sex, race/ethnicity, education, income, language, country of origin, time in US, others	■				
Health status (physical, mental)	Promis – anxiety & depression, global, physical	■				
Cognitive status	BTACT	■			■	
Social support	TSS; Medication Support Survey	■			■	
Health literacy	NVS, Chew	■			■	
Patient activation	CHAI	■			■	
Regimen characteristics	MRCI, drug class, cost	■		■	■	■
System Process Outcomes						
Receipt of UMS materials	Receipt of UMS (yes/no)		■	■	■	■
Medication reconciliation	Updates to medical/pharmacy records				■	
Receipt of SMS text reminders	Receipt of SMS (yes/no), satisfaction		■	■	■	■
Completion of assessment	Completion of assessment, satisfaction		■		■	
Clinic follow-up	Did clinic follow up on concerns		■		■	
Intervention impact on clinic practice	Qualitative interview with clinic staff					
Patient Effectiveness Outcomes						
Medication adherence	ASK-12, 24hr recall	■	■	■	■	■
	Pill Count	■		■		
	Proportion of Days Covered, Tacrolimus Levels			■	■	■
Treatment knowledge	General Rx knowledge, Demonstrated use, Consolidation	■	■	■	■	■
Quality of Life	PROMIS (physical, anx, dep, global)					
Clinical outcomes	Transplant related: eGFR, re-hospitalization, IFTA, acute rejection, toxicity, infection					
	Systolic blood pressure, Hemoglobin H1AC	■		■	■	
Cost Outcomes						
Programming maintenance costs for EHR	Printer ink, paper, staff time					
Running UMS technologies						
SMS monthly costs						

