### **9.10 Intervention: TAKE IT Strategy.**

Our strategy is a multifaceted intervention that leverages the existing resources of a transplant center and increasingly available provider and patient-facing technologies to

simplify KT recipients' role in managing complex, multi-drug regimens and monitor use over time. The goal of the TAKE IT strategy is to optimize adherence and to detect problems earlier in order to improve health outcomes – both in transplant-specific conditions and for comorbidities. This approach is multifaceted, yet highly scalable due to minimal costs and impact on existing transplant center workflow. It includes the following 4 components:

1. **A routine adherence assessment** that requests patients to periodically report upon their medication use, providing a continuous link between the transplant center and patient beyond routine in-person visits. This assessment will routinely identify patients at risk of non-adherence and categorize the nature of their adherence concern in one of the following areas: cognitive, psychological, regimen, medical, social, economic.
2. **Care Alert Notifications** directed to the transplant center nurse coordinator if an adherence related problem is identified by the routine adherence assessment, who can then activate appropriate staff to respond.
3. **Quarterly adherence reports** that will automatically calculate a coefficient of variance for patients' tacrolimus levels at routine intervals and impart results to transplant nurse coordinators.
4. **Tailored clinical support** leveraging transplant center tools to directly target the adherence-related concern identified by the routine adherence assessment. The study team will focus on leveraging existing transplant center resources, including clinical consultation with pharmacists, social workers and transplant nurse coordinators, as well as existing technological and educational tools. These tools will be bundled and initiated in response to specific patient-reported adherence concerns.

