**11.0 Data and Specimen Management:**

**11.1 Analysis Plan.**

All analyses will be performed in SAS v9.4 (SAS Institute, Cary, NC). [name] will perform analyses under the direct supervision of Drs. [name], [name] and [name]. Drs. [name] and [name] will also provide guidance.

Aim 1.

The proposed trial uses a 1:1 randomized design that assigns patients to TAKE IT or usual care within each cohort. We will accrue approximately 700 patients (350 de novo, 350 established) anticipating 90% retention in the de novo cohort (85% established) for follow-up at 1 year, leaving a minimum 525 patients for primary analyses. High retention will be supported through close follow-up, mailed reminders, birthday cards, and a newsletter. Given the clinical follow-up necessary for KT recipients, we are confident we will achieve this goal.

Regimen adherence at one year is the primary outcome of interest for Aim 1, with Rx knowledge and individual adherence measures also of primary interest. Secondary outcomes include quality of life (PROMIS outcomes and FKSI) and the clinical outcomes of change in eGFR, and any transplant-related re-hospitalization. Blood pressure control in those taking anti-hypertensive medications will also be examined. Relationships between

adherence and potential confounders (age, comorbidity, cognitive ability, regimen complexity, internet use, dose of intervention, etc.) will also be examined. For all outcomes, we will use generalized linear models (GLMs), adjusted for confounders and study site, specifying the logit link function for binary outcomes and identity link for continuous outcomes (quality of life, change in eGFR, SBP). Treatment group will be the independent variable of primary interest, with usual care specified as reference group. We will also include time since transplant at baseline (in months), baseline value of the outcome, and any potential confounding covariates noted in bivariate analysis. For outcomes measured per medication, a generalized estimating equation (GEE) approach will be employed to adjust standard errors for within-patient correlation. Should TAKE IT have an effect on outcomes, secondary analyses will examine if any of the potential confounders considered exhibit any effect modification.

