### Aim 2.

Generalized linear mixed models (GLMMs) will be used to examine intervention effects over the course of the study. Link functions will be included as described above for the GLM models. Adherence concerns may differ in the two cohorts, thus separate models will be employed for each cohort (de novo, established). Treatment group will be the independent variable of primary interest, modeled as a fixed effect with the usual care group specified as reference group. We will also include fixed effects for site (NU, Mayo), time since transplant (in months), and potential confounding covariates noted in bivariate analyses. Random participant effects for each participant will be included to account for repeated measurements nested within each participant (assuming a compound symmetry, although we will fit autoregressive structures as well, comparing fit using AIC and BIC criterion). Outcomes recorded at each interview will be analyzed by visit whereas adherence measured by tacrolimus levels, along with blood pressure control will be analyzed in 6-month intervals as described above. A time-since-transplant-by-arm interaction term will be included to examine if outcome trajectories/slopes over time differ by study arm. Since prescription knowledge and adherence will be assessed for each medication, 2-level GLMM will be used for these outcomes with medications nested in participants. For  $\Delta$  eGFR and re-hospitalization outcomes, GLM models will be used since outcomes over 2 years are summarized in a single measurement. In the de novo cohort, change in eGFR from transplant to 2 years post-transplant and # hospitalizations (any hospitalization, if rare) within 2 years post-transplant will be modeled. For the established cohort, the time period for the both measures will span from transplant to 2-year study visit. It is possible those who do not complete the 2-year visit will differ in important characteristics (e.g. cognition, comorbidity), which could bias results. We will use collected data at prior interviews to understand the extent that individuals who complete follow-up differ from those who do not. If differences are found, pattern-mixture models will be employed by classifying participants' drop-out type or pattern (e.g. completed, refused, lost to follow up, death). This variable will then be added to mixed effects models to account for differences.

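### Intervention dose, a consequence of the assigned arm, is listed as a potential confounder that may enter the Aim 1 models; if it does, the arm coefficient no longer estimates TAKE IT versus usual care

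*Combined protocol and SAP*

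**What the plan says.** In section 11.1, Aim 1, the plan states that relationships between "adherence and potential confounders (age, comorbidity, cognitive ability, regimen complexity, internet use, dose of intervention, etc.) will also be examined". For all outcomes it continues: "we will use generalized linear models (GLMs), adjusted for confounders and study site". Besides treatment group, the models take time since transplant at baseline, the baseline value of the outcome, and "any potential confounding covariates noted in bivariate analysis". If TAKE IT has an effect, "secondary analyses will examine if any of the potential confounders considered exhibit any effect modification".

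Aim 2 repeats the screening rule, with fixed effects for "potential confounding covariates noted in bivariate analyses", but does not name dose.

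Dose is not defined anywhere. The nearest measures are in section 8.3, which collects app use, portal use and the number of completed adherence assessments as process measures. Section 9.10 describes care alerts "directed to the transplant center nurse coordinator if an adherence related problem is identified by the routine adherence assessment", and says of the support tools: "These tools will be bundled and initiated in response to specific patient-reported adherence concerns".

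No sentence limits the screened covariates to baseline values. Two other items on the same list are recorded again after baseline in Table 4 (section 8.0): cognitive status, and regimen characteristics ("MRCI, drug class, cost").

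**The concern.** A confounder of a randomised comparison would have to precede assignment. Dose follows from it: section 9.7 has TAKE IT components started for those randomised to receive them, and section 9.11 says that neither site has an active self-care portal in usual care. Adjusting for dose therefore conditions on something that the treatment caused.

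The Aim 1 arm coefficient is the trial's main result, on adherence at one year. If dose enters that model, the size of the coefficient, and in some settings its sign, depends on how dose is defined and on which patients accrue it. The choice is left to a bivariate screen with no stated threshold. A variable that captures diligence, or the mechanism of the intervention, is the kind that such a screen tends to pick up.

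**Working it through.** **1. What the arm coefficient becomes.** Write logit P(non-adherent) = b0 + b1·arm + b2·dose.
- Dose coded 0 in usual care: b1 compares TAKE IT patients at zero dose with all usual-care patients. That is not the randomised contrast.
- Dose coded missing in usual care: a complete-case fit loses the control arm.
- Effect modification with dose 0 in usual care: arm × dose equals dose, so the interaction cannot be separated from the main effect.

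**2. The plan's own power figures.** From the Power Calculation: 305 per arm, 45% non-adherent in usual care, an 11-point difference (45% to 34%, odds ratio (0.34/0.66)/(0.45/0.55) = 0.63), 5% error taken as two-sided.
- z = 0.11 / √(2 × 0.395 × 0.605 / 305) = 2.779
- Power = Φ(2.779·√(1 − R²) − 1.96)
- R² = 0: Φ(0.819) = 79% (plan: at least 80%)
- R² = 0.2: Φ(0.526) = 70% (plan: 70%)

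Both figures reproduce.

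**3. Precision if dose enters and is unrelated to outcome given arm.** The documents give no uptake figures, so these are assumed. TAKE IT dose is the share of 12 monthly assessments completed, Binomial(12, expit(a + s·u))/12, where u is a standard normal diligence trait. Usual care is 0. With 1:1 allocation, R² = m²/(m² + 2v), where m and v are the mean and variance of dose in TAKE IT.

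| Mean dose (s) | SD of dose | R² | Power |
|---|---|---|---|
| 24% (3.0) | 0.317 | 0.0576/(0.0576 + 0.2010) = 0.22 | 69% |
| 43% (2.0) | 0.329 | 0.1849/(0.1849 + 0.2165) = 0.46 | 53% |
| 33% (0.8) | 0.204 | 0.1089/(0.1089 + 0.0832) = 0.57 | 45% |
| 65% (0.8) | 0.208 | 0.4225/(0.4225 + 0.0865) = 0.83 | 21% |

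Usual care need not be at 0. Section 9.9 offers the reminder app after the baseline interview with no stated arm restriction. With TAKE IT at 65%, a usual-care mean of 10% gives R² 0.73 and power 30%; a usual-care mean of 25% gives R² 0.51 and power Φ(2.779 × 0.70 − 1.96) = 49%. In the other three patterns above and the two alert-triggered patterns in step 4, usual care at 25% gives R² of 0.00-0.11 and power of 75-79%.

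**4. Direction of bias.** Logistic simulation, 305 per arm, true risks 45% and 34% (odds ratio 0.63), usual-care dose 0. The link is the log-odds of adherence per SD of u (0.2, 0.4 or 0.6). A baseline value correlated 0.7 with u is in the model. All of these settings are assumed.

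| What dose reflects | Arm odds ratio with dose in the model |
|---|---|
| Effect wholly through dose, link 0 | 0.99-1.01 |
| More diligent patients take up more (mean 24-65%), links 0.2 / 0.4 / 0.6 | 0.68-0.85 / 0.73-1.09 / 0.77-1.45 |
| Support triggered by poor adherence (mean 21% or 39%, s = −0.8), same links | 0.53-0.56 / 0.44-0.51 / 0.36-0.45 |

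**5. With an assumed p<0.05 screen.**
- Effect wholly through dose: dose enters in 87-100% of trials, and significant benefit remains in 2-4%.
- More diligent patients take up more: dose enters in 70-100%. Significant benefit is found in 7-55 / 2-38 / 0-27% at the three links, against 78-82% without dose. With no true effect, false harm is 2-4 / 7-18 / 19-44%, against 2.5% nominal.
- Alert-triggered: dose enters in only 6-32%. Significant benefit is 68-87% against about 80%, so the test changes little. With no true effect, false benefit is 3 / 9-11 / 23-30%.

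**The case against.** The sentence that names dose says only that relationships with adherence will be examined, which can be read as a descriptive look at correlates. Several places suggest that the authors had pre-treatment covariates in mind:
- Section 8.2 gives the reason for covariates as possible imbalance between randomised groups, and neither it nor the covariate block of Table 4 includes dose.
- Section 8.3 files uptake under fidelity, and the Aim 3 analysis plan gives fidelity its own exploratory analysis.
- The Power Calculation calls an R-squared of 0.2 conservatively high under randomisation, which makes sense only for baseline covariates.
- Section 9.7 blinds the analysts, and a dose variable that is zero throughout one arm would reveal allocation.
- Sections 9.4 and 12.1 give the DSMB the task of approving the analysis plan.

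All of this stands as evidence of a drafting slip, and it makes entry possible rather than expected. It does not remove the problem. The model and effect-modification sentences use the same term as the list, and no written rule keeps dose out.

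It is also fair that the magnitudes rest on assumed uptake, selection and links. At the weakest link (0.2) with no true effect, error stays near nominal. A separate set of assumptions (mean dose about 0.6, link 0.8 in either direction, no baseline value, no true effect) gave arm odds ratios of 4.91 and 0.20. The size is therefore open; the structural point is not.

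**Conclusion.** Wrong as written, and probably a drafting slip. Applied literally, the Aim 1 rule allows a consequence of assignment into the primary between-arm model and requires it to be considered as an effect modifier.

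Three stronger readings are tempting and not supported:
- That the plan will adjust for dose. Dose and the screening threshold are both undefined, and Aim 2 does not name dose at all.
- That the bias has one known direction. The documents support measures that would push it either way: completed assessments plausibly track diligence, while alerts and tailored support follow adherence problems.
- That arm-dose R-squared will exceed 0.2. That depends on usual care having zero or low dose. If usual-care patients accrue comparable dose, for example through the app, the precision loss is small.

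The conditional conclusion holds. If dose enters, the arm coefficient is no longer the randomised contrast. Under the stated assumptions, a true odds ratio of 0.63 can appear anywhere from about 0.36 to 1.45. Without bias, and with no dose in usual care, power falls to between 69% and 21%.

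**What to change.** In section 11.1, Aim 1, delete intervention dose from the list of potential confounders. Add that only baseline covariates may be adjusted for, or tested as effect modifiers, in the between-arm models of Aims 1 and 2. Define these as values collected at or before the baseline interview, including the baseline value of the outcome. Except from this the time terms and the drop-out-pattern variable that Aim 2 already plans.

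The wording should refer to baseline rather than to values recorded before randomisation. The study timeline (Table 2, section 7.0) lists randomisation ahead of baseline interviews, so a strict pre-randomisation rule could bar the baseline outcome value that Aim 1 requires. The baseline rule also settles which values of cognition and regimen complexity are used.

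Keep dose, once defined, for the exploratory fidelity analysis in Aim 3. That analysis is planned only if delivery problems occur, so one more clause is needed if the dose-response question is wanted in any case.

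The cost is about two sentences and that optional clause, with no new data, visits or sample size.

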#### **2.4 Preliminary Data: Prevalence of Transplant Adherence and Barriers.**

We recently conducted interviews with 99 KT recipients at Northwestern and Emory Universities. 24% of participants had limited literacy. Patients were taking an average of 11 (SD=4) medications; one third (32%) had a medication change in the past month. 1 in 4 KT recipients could not demonstrate proper regimen use for IS regimens and 35% were poorly adherent based on self-report or by tacrolimus level standard deviation. In multivariable analyses, fewer months since transplant and limited literacy were associated with poor adherence (all  $p < 0.05$ ). In multivariable models, patients over 65 (OR 2.45, 95%CI 1.20-4.98), non-white race (OR 2.83, 95% CI 1.54-5.20), demonstrating improper regimen use (OR 1.15, 95% CI 1.01-1.30) and inadequate adherence (OR 2.10, 95%CI 1.10-4.01) had a higher post-transplant hospitalization risk.

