## 8.2 Covariates.

Patient Characteristics. We will include a socio-demographic/health questionnaire, the Tangible Social Support survey to assess the extent/quality of social connections, healthcare support will be measured using the Medication Support Survey. The Brief Test of Adult Cognition by Telephone (BTACT) and the Consumer Health Activation Index (CHAI) will also be included.

Literacy Assessment: Newest Vital Sign (NVS). Patients are given a copy of a nutrition label and asked 6 questions about how they would interpret and act on the information. Scores are classified as high likelihood of limited literacy (0-1), possibility of limited literacy (2-3), and adequate literacy (4-6).

Regimen Characteristics. Self-reported medications will be collected and grouped into drug class. These will capture important covariates that may be related to outcomes and unequally distributed among randomized subjects.

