*Power Calculation.* The sample size calculation was based on the availability of 700 transplant patients estimated by the number of transplants conducted in 2012-2014 across the two sites. With the sample size set at 610 accounting for 85-90% retention at 1 year, we present the minimum differences we will be able to detect between the intervention and usual care arms for each outcome of interest. For the main outcome of medication adherence, we estimate 45% of the sample to be non-adherent using the composite score described above taking estimates for each individual measure into account. We will have sufficient power ( $\geq 80\%$ ) to detect differences of 11% in the entire sample assuming a 5% Type I error rate. Should TAKE IT be associated with potential confounders, calculations show that an R-squared of 0.2 between predictors (a conservatively high estimate under randomization), we would still maintain 70% power to detect the 11% difference. Although adjusting for confounders would decrease variability in adherence, and increase power. Detectable differences for individual adherence measures along with estimates and effect sizes for other outcomes of interest are listed in Table 5.

Table 5. Detectable Differences in Health Outcomes between Study Arms at 1 Year

Outcome	Total (n=610) 305/arm		De Novo (n=270) 135/arm		Established (n=340) 170/arm	
	Usual Care Estimate	Minimum Difference	Usual Care Estimate	Minimum Difference	Usual Care Estimate	Minimum Difference
Primary Outcomes						
Rx Knowledge, %	50	11.3	60	15.9	45	15.1
Rx Non-adherence, %	45	11.0	35	15.2	50	15.0
Self-report, %	35	10.3	29	14.1	44	14.6
Objective (pill count), %	45	11.1	35	11.3	50	15.0
Claims (PDC), %	30	9.8	23	12.7	38	14.0
Biologic (SD Tacrolimus), %	40	10.8	30	14.3	45	14.7
Secondary Outcomes						
Quality of life, mean(SD)	46.2 (9.0)	2.0	45.8 (7.2)	2.5	49.5 (9.0)	2.7
Clinical outcomes						
$\Delta$ eGFR, mean(SD)*	-5.8 (9.0)	2.9	-3.0 (11.0)	3.8	-8.0 (15.0)	4.6
Re-hospitalizations, %	40	10.8	32	14.6	47	14.8
Systolic BP, mean(SD)**	136.7 (8.3)	2.2	138.3 (12.9)	5.1	135.0 (7.9)	2.8

\* $\Delta$  eGFR estimates over 2 years

[figure not shown]
\*\*estimate 75% of cohort has hypertension (Total: n=458, 229/arm; De Novo: n=202, 101/arm; Established: n=256, 128/arm)

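### The adjustment covariates for the arm comparison should be a baseline set named in advance, not the result of an undefined bivariate screen whose candidates include a post-randomisation variable

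*Combined protocol and SAP*

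**What the plan says.** Section 11.1, Aim 1, specifies generalized linear models "adjusted for confounders and study site". It continues: "We will also include time since transplant at baseline (in months), baseline value of the outcome", and then adds "any potential confounding covariates noted in bivariate analysis". Site, time since transplant and the baseline outcome are therefore always in the Aim 1 model, and everything else depends on the screen. The named candidates are "age, comorbidity, cognitive ability, regimen complexity, internet use, dose of intervention, etc", so the list is open-ended. Health literacy is not among the named examples. Aim 2 fixes site and time since transplant and then repeats the rule with "potential confounding covariates noted in bivariate analyses".

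No threshold is given. Nor does the plan say whether one selected set serves all outcomes.

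The direction of the test is also unclear:

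- Aim 1 speaks of examining how the candidates relate to adherence, which suggests a test against outcome.
- The Power Calculation considers the case where TAKE IT is associated with potential confounders, which suggests a test against arm.
- Section 8.2, in its paragraph on regimen data, speaks of "important covariates that may be related to outcomes and unequally distributed among randomized subjects", which can be read the same way.

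The Power Calculation also says that "adjusting for confounders would decrease variability in adherence, and increase power". Section 2.4 reports from the pilot that "fewer months since transplant and limited literacy were associated with poor adherence". Table 4 marks age (under socio-demographics), NVS, BTACT and MRCI at baseline.

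**The concern.** Confounding of arm by a baseline variable cannot arise systematically under 1:1 randomisation; any imbalance is chance. A screen that asks whether a covariate is imbalanced therefore keeps or drops it by luck, whatever its prognostic value. A screen against outcome selects better. It still picks the model after the outcomes are seen, and it can give a different model for each outcome.

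The open list brings a second problem. Dose of intervention is determined after randomisation and is tied to arm. If it entered the arm-comparison model, the treatment coefficient would no longer measure the effect of assignment to TAKE IT.

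At stake are some precision, protection against choosing among several defensible models, and the meaning of the primary estimate.

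**Working it through.** **1. The plan's own power.** Inputs from the Power Calculation and Table 5: 305 per arm, 45% against 34% non-adherent, alpha 5% (two-sided assumed). Mean risk = (0.45 + 0.34)/2 = 0.395.

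- Null SE = √(2 × 0.395 × 0.605 / 305) = 0.0396.
- Alternative SE = √((0.45 × 0.55 + 0.34 × 0.66) / 305) = 0.0393.
- Power = Φ((0.11 − 1.96 × 0.0396) / 0.0393) = 0.795, against the stated 80% or more.
- With R-squared 0.2 between arm and covariates, 305 × 0.8 = 244 per arm gives 0.702, against the stated 70%.

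Both figures reproduce to rounding.

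**2. Chance that literacy is dropped by a screen on arm.** Under randomisation this is 1 − threshold: 95% at p<0.05, 90% at p<0.10, 80% at p<0.20, whatever its prognostic strength.

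**3. Chance that it is kept by a screen on outcome.** The documents give 24% limited literacy (Section 2.4) but no odds ratio for adherence, so 1.5 to 3 is assumed. Of 610 patients, 0.24 × 610 = 146 have limited literacy and 464 do not; overall non-adherence is 39.5%. For odds ratio 2 the risks are 52.3% and 35.4%, and the two-proportion test at p<0.05 has power 0.952. The table shows the other cases.

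**4. Power gained by forcing literacy in.** Logistic models were simulated with 610 patients and 3,000 trials per setting. Marginal risks were set at 45% and 34%, and literacy was also related to baseline non-adherence. The strength of the baseline outcome is not in the documents, so odds ratios of 1 and 4 were assumed. Each arrow runs from the model without literacy to the model with it, on the same simulated trials.

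| Literacy OR | Kept, outcome screen p<0.05 | Kept, p<0.20 | Power, baseline OR 1 | Power, baseline OR 4 |
|---|---|---|---|---|
| 1.5 | 0.564 | 0.797 | 0.804 → 0.809 | 0.848 → 0.853 |
| 2 | 0.952 | 0.990 | 0.806 → 0.812 | 0.850 → 0.856 |
| 3 | 1.000 | 1.000 | 0.810 → 0.823 | 0.856 → 0.870 |

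Forcing literacy in gains 0.5 to 1.4 points over omitting it. Against forcing it in, a screen on arm (p<0.05 or p<0.20) loses about 0.2 to 1.4 points and a screen on outcome about 0 to 0.1.

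**5. A larger fixed set.** If the set explains an extra share R² of outcome variance beyond the terms already fixed, effective size per arm is about 305/(1 − R²). Power rises from 0.795 to 0.803 (R² 0.02), 0.815 (0.05), 0.835 (0.10) or 0.876 (0.20). This approximation is generous for a logistic model. Literacy at odds ratio 3 has R² 0.054, for which the formula implies about 2 points, against 1.3 to 1.4 simulated. The documents give no R² with outcome.

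**6. Type I error.** With no treatment effect (6,000 trials, literacy odds ratio 2 or 3, baseline odds ratio 4), every rule gave 0.047 to 0.052.

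**7. Dose of intervention.** Suppose dose is zero under usual care, and write the linear predictor as a + b·arm + c·dose. Then b compares TAKE IT patients at zero dose with usual care. The part of the effect that works through delivery of the intervention moves into c, so b is not the effect of assignment. A screen on arm would be expected to flag dose.

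**The case against.** The strongest reply is that the screen is most naturally read as one on outcome. The only description of the examination, in Aim 1, relates candidates to adherence. The Section 8.2 sentence explains why regimen data are collected and is not a selection rule. On that reading a strong predictor is mostly kept and almost no power is lost. This stands, though the Power Calculation wording leaves the other reading open.

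It is also fair that the likely main predictors are already fixed in Aim 1, including time since transplant, the other predictor found in the pilot. Age, cognition and regimen complexity are named candidates, and an open-ended list does not exclude literacy. This stands too. A qualification is that Table 4 appears to show claims-based adherence and tacrolimus levels only from 6 months, so a baseline value of the composite may not exist.

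Section 9.7 blinds the analysts and principal investigators, and Sections 9.4 and 12.1 have the DSMB approve the analysis plan. These are real safeguards. They do not supply the missing threshold, direction or list, and they do not make dose of intervention a baseline variable.

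Three stronger readings are tempting and are not supported:

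- A reader might infer that literacy would usually be dropped. That holds only for a screen that considers arm.
- A reader might infer that a fixed set would raise power to 82–85%. A simulation with 12 candidates, six of them prognostic, gave 0.820 and 0.845 against 0.79 under a screen on both arm and outcome. It did so only by assuming joint R-squared of 0.10 and 0.20, which have no source in the documents.
- A reader might infer an inflated type I error. In the same simulation it reached 5.5 to 7.3% only if the most favourable of several models were reported, which the plan does not propose.

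**Conclusion.** The point holds as a low-cost improvement to the analysis plan, not as a threat to the trial's validity. The selection of covariates beyond those already fixed is open in direction, threshold and candidates. It depends on the observed outcomes, can differ between outcomes, and gives a known pilot predictor no assured place. The power argument is secondary: for literacy it is worth roughly one point, and for a larger set it depends on a quantity that the documents do not give. The case for change rests mainly on removing model choice made after outcomes are seen, and on keeping a post-randomisation variable out of the effectiveness model. The figures assume a two-sided test, 24% limited literacy as in the pilot, and the odds ratios stated above.

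**What to change.** In Section 11.1, replace the bivariate-screening clause under Aim 1 and Aim 2 with one covariate set, fixed before unblinding and used for every outcome:

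- study site;
- time since transplant at baseline;
- baseline value of the outcome, where collected;
- baseline age, NVS health literacy, BTACT cognition and MRCI regimen complexity.

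State that the baseline values are meant, since Table 4 also marks NVS, BTACT and MRCI at later visits. In Aim 2, keep the existing time-since-transplant term and its interaction with arm. Use the baseline outcome as a covariate there only if it is not also one of the modelled repeated measurements.

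Exclude dose of intervention and any other post-randomisation variable from the arm-comparison model; dose can be studied in the Aim 3 fidelity analyses. Add a simple rule for missing baseline covariates, such as single imputation or a missing indicator. It is needed because the NVS uses a printed label (Section 8.2) while Mayo baseline measures may be taken by phone (Section 9.9). Report the unadjusted estimate as a sensitivity analysis.

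The cost is a change of wording and a few degrees of freedom at n=610. No new data are needed.
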